7.2 PARTICIPANT DISCONTINUATION/WITHDRAWAL FROM THE STUDY

Participants are free to withdraw from participation in the Study at any time. If the withdrawal happens during the Treatment /Follow up Phase, the last visit prior to withdrawal will be treated as EOT/EOS visit and corresponding CRF will be completed by the Investigator.

Subjects who sign the informed consent form (ICF) and are randomized but do not receive the study intervention will not be replaced and will not be part of ITT Population.

Subjects who sign the ICF, and are randomized and receive the study intervention, and subsequently withdraw, or are withdrawn or discontinued from the study, will not be replaced and yet be part of ITT Population.

Subjects must be discontinued from the Study after randomization if any of the following events occur (Stopping or Discontinuation Rules for Individual Subjects):

1. A Subject withdraws consent
2. Investigator recommends that the Subject should discontinue the participation in the Study
3. Subject misses two consecutive Weekly Visits during Treatment Phase
4. If the Target Ulcer and the adjoining wound merge together and if the Investigator opines that following the Target Ulcer is difficult. A detailed note by the Investigator will be recorded in the e-CRF outlining reasons for such merger in line with the preceding measurement of Target Ulcer
5. If Subject requires hospitalization for more than two consecutive weeks during the Study
6. The Subjects with treatment compliance of less than 80% or more than 120% during the week, will be considered treatment non-compliant for that week. If such non-compliance is observed for more than three weeks, and if the blinded Investigator opines that it may affect the outcome of the Study, then the Subject shall be considered non-compliant for the Study and shall be discontinued from the Study
7. If the blinding of a Subject is compromised
8. Any form of major protocol violation
9. The Target Ulcer increases in size (more than 30%) for two consecutive weeks or requires deep, surgical debridement for more than two occasions during the Treatment Phase to address Target Ulcer deterioration
10. The Target Ulcer becomes infected requiring topical antimicrobial treatment
11. If Subject develops osteomyelitis or cellulitis during the Study on the foot having the Target Ulcer
12. If female Subject becomes pregnant, during the study
13. If Subject misses 6 consecutive dressings

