Target Ulcer classification and its measurement: Classification of all the potential Target Ulcers and its measurement will be completed as per Texas system at the screening visit (V1). The classification and measurement will be done for selected Target Ulcer at Baseline Visit (V2) as well as in all Treatment and Follow-up Visits (V3 to V18) (See Attachment 1). The measurement of the Target Ulcer area will be done using advance camera. The parameters captured will be area, volume, mean depth and maximal depth. It should however be noted that volume and depth measurements may be inaccurate to the extent of the advance camera's technical limitations. In the event of inability to measure wound size by advance camera, the Target Ulcer area measurement will be done with the help of wound tracing in conjunction with planimetry software. In such situation, only Target Ulcer area will be measured.

Target Ulcer characteristics: Assessment of Target Ulcer characteristics in terms of wound edge, color, drainage amount and type, peri-wound conditions and color and percent wound bed covered by granulation tissue, fibrin slough, and necrotic tissue will be done at all Visits (V1 to V18).

Wound Care: Wound care to be taken during the Study will be explained to the Subject by the Investigator at the time of Screening and periodically. This will include following:

1. A moist wound environment as suitable for the condition of wound (moist bandage should not be used in case wound is oozing and highly moist)
2. Non-adherence of dressing to the wound
3. Allowance for removal of dressing from the wound without pain or trauma
4. Role of the dressing to absorb the excess wound exudates
5. Allowance for gaseous exchange through the protective dressing
6. Prevent permeance to microorganisms

Debridement of Target Ulcer: Debridement of the Target Ulcer, if required along with documentation of type of debridement (e.g. callus removal, sharp or surgical), reason for debridement will be recorded at Screening Visit V1 and all treatment and Follow-up visits V2 to V18 (as and when necessary).

The Target Ulcer will be surgically debrided, if required as per procedure given below.

1. Perform sharp debridement to remove all necrotic soft tissue, hyperkeratotic wound margins, bacterial burden, cellular debris, sinus tracts, fistulae, undermined borders, and callus to produce viable wound margins and a clean ulcer site.

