Approximately 5 mL blood will be collected from each Subject at visits where laboratory assays are to be performed. These visits are Screening visit V1, V6, V10, V14 or EOT visit whichever is earlier and V18 or EOS/FU4 whichever is earlier. The laboratory assessments are haematology, biochemistry and HbA1c. Thus, total volume of blood that will be withdrawn per Subject during the Study will be approximately 25 mL.

Any additional/unscheduled investigation(s) can be done at the Investigator's discretion as needed. These investigations may also be done at local laboratory, if required.

Urine pregnancy test will be done locally in women of child bearing potential at Screening Visit V1, V6, V10, V14 or EOT whichever is earlier, and V16/FU2 at Follow-Up.

ECG and X-ray: ECG will be done at Screening Visit V1, and every 4 weeks after Baseline during Treatment visit V6, V10, and V14 or EOT and V15/FU1 at follow-up. X-ray of the foot under Study will be performed at the Screening Visit and further at the Investigator's discretion to rule out osteomyelitis.

Recording and Assessment of adverse events: if there is any clinically significant abnormality or signs or symptom detected in the Subject or reported by the Subject after the application of treatment, it will be recorded as an adverse event. The AE assessment will be done from Baseline Visit V2 to V18 or EOS/FU4, whichever is earlier.

Assessment of local pain: Local pain at the Target Ulcer site will be measured in terms of 11-point universal pain scale as mentioned in *Attachment 4*.

Assessment of local edema: Local edema at the Target Ulcer site will be measured in terms of 5-point edema scale as mentioned in *Attachment 4*.

Assessment of local erythema: Local erythema at the Target Ulcer site will be measured in terms of 5-point erythema scale as mentioned in *Attachment 4*.

The local pain, edema and erythema will be recorded at all the visits from Baseline Visit V2 to V18 or EOS/FU4, whichever is earlier.

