8.2.4 TIME PERIOD AND FREQUENCY FOR EVENT ASSESSMENT AND FOLLOW-UP

The occurrence of an adverse event (AE) or serious adverse event (SAE) may come to the attention of Study personnel during Study visits or Study Nurse during visits to Subject and interviews of a Study Subject presenting for medical care, or upon review by a study monitor.

All AEs including local and systemic reactions not meeting the criteria for SAEs will be captured on the appropriate electronic case report form (eCRF). Information to be collected includes duration (start and end dates), severity/intensity, relationship to IP, specific therapy, results and consequences and seriousness. All AEs occurring while on Study must be documented appropriately regardless of relationship. All AEs will be followed to adequate resolution.

Any medical condition that is present at the time that the participant is screened or before application of first dose will be considered as baseline and not reported as an AE. However, if the Study participant's condition deteriorates at any time during the study, it will be recorded as an AE.

Changes in the severity of an AE will be documented to allow an assessment of the duration of the event at each level of severity to be performed. AEs characterized as intermittent require documentation of onset and duration of each episode.

The Investigator will record all reportable events with start dates occurring any time after informed consent is obtained till the last day of Study participation. At each Study visit, the Investigator will inquire about the occurrence of AE/SAEs since the last visit. Events will be followed for outcome information until resolution or stabilization. An AE can reach one of the following outcomes:

- a. Complete recovery (AE/ SAE end date will be captured).
- b. Recovered with sequelae. (AE/ SAE end date will be captured and the sequelae will be specified).
- c. Ongoing
- d. Death
- e. Unknown: The outcome of the event may be captured as unknown only in the exceptional cases when the Subject is lost to follow-up (AE end date will be left blank).

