8.2.5 ADVERSE EVENT REPORTING

AEs will be assessed during each visit by doing clinical examination, review of the laboratory investigations and by directly questioning the Subject/LAR/impartial witness. The increase of Target Ulcer size or its worsening will be considered as adverse event. The change from Baseline in laboratory values, vital signs and ECG/EKG parameters outside accepted or normal range will be reported as adverse event irrespective of Investigator's opinion on clinical significance of such abnormality.

As far as possible each AE should be described to include:

- Duration (start and end dates)
- Severity/Intensity
- Relationship to IP or Specific therapy
- Results and Consequences
- Seriousness

Those AEs that are already documented in the CRFs, at a previous assessment and designated as 'ongoing' would be reviewed at subsequent visits, as necessary. If these have resolved, the documentation in the CRF would be completed.

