8.2.7 EVENT NOT TO REPORTED AS AE

Progression of underlying disease (at Investigator's discretion) / Study indication/lack of efficacy of the IP would NOT be reported as an AE/SAE.

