9.4.4.1 TREATMENT EMERGENT ADVERSE EVENT

Treatment emergent adverse events (TEAE) are undesirable events not present prior to medical treatment, or an already present event that worsens either in intensity or frequency following the treatment. The TEAEs, which is defined as all AEs on or after the application of first dose of IP will be summarized according to the numbers and percentages of TEAEs as well as numbers and percentages of Subjects with one or more occurrences of TEAEs during the Study. Number of Subjects with TEAEs and number of events of TEAEs will be tabulated by preferred term (PT) and system organ class (SOCL). If a Subject had more than one TEAE, event will be counted only once in SOCL and once for each PT.

Summaries of TEAEs by severity grade, relationship to Study medication, leading to death, SAEs of study, IP related TEAEs will be provided.

Also, summarization for SAE, SAEs by severity, SAEs by relationship to Study IP will be provided separately.

Listing will be provided for all Subjects who have at least one adverse event.

AEs will be coded using the MedDRA, version 20.0 or later.

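### Sections 8.2.5 and 8.2.7 conflict on whether an enlarging Target Ulcer is an adverse event, and 8.2.5 as written lets measurement noise and slow healing into the TEAE endpoint

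*Combined protocol and SAP*

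**What the plan says.** Section 8.2.5 names the Target Ulcer directly: "The increase of Target Ulcer size or its worsening will be considered as adverse event". It gives no minimum change, no visit to compare with, no debridement state and no confirming measurement. Section 8.2.4 points the same way: "if the Study participant's condition deteriorates at any time during the study, it will be recorded as an AE".

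Section 8.2.7 points the other way: "Progression of underlying disease (at Investigator's discretion) / Study indication/lack of efficacy of the IP would NOT be reported as an AE/SAE". Section 8.1 adds a qualifier to AE recording in general: "if there is any clinically significant abnormality or signs or symptom detected in the Subject or reported by the Subject".

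Section 9.4.4.1 then counts as treatment-emergent every AE from first dose onward: "The TEAEs, which is defined as all AEs on or after the application of first dose of IP". The subject-level proportion with TEAEs is the Galnobax safety endpoint in Section 3.

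The protocol does use a margin and a debridement state elsewhere, but for other purposes. Section 7.2 item 9 lists as a reason for discontinuation: "The Target Ulcer increases in size (more than 30%) for two consecutive weeks". Section 5.1 fixes ulcer area as post-debridement for eligibility. Neither is carried into the AE rule.

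**The concern.** The ulcer is measured at Baseline and at up to 12 weekly treatment visits. If any measured rise is an AE, the event threshold equals the ulcer's current state, and an ulcer that never grows can cross it through measurement error alone. Slow healers stay open for more visits and shrink less between visits, so they cross it more often. If Galnobax heals faster, its TEAE proportion would then be lower for reasons unrelated to safety.

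The conflict with 8.2.7 is a separate problem. One investigator may record an enlarging ulcer under 8.2.5, while another treats it as progression or lack of efficacy under 8.2.7. About 40 sites are planned, so the endpoint would also mix recording conventions.

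**Working it through.** **1. The passages side by side.** An ulcer that grows is an AE under 8.2.5 and 8.2.4, and may be a non-AE under 8.2.7. No section gives an order of precedence. Section 8.2.5 waives clinical significance explicitly for laboratory values, vital signs and ECG, but is silent on this for ulcer size. It is therefore also unclear whether the qualifier in 8.1 applies.

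**2. Inputs.** From the plan: weekly measurement over 12 weeks (4.1), and closure by week 12 of 39% on SoC and 60% on Galnobax (9.2). The plan gives no figure for ulcer-size AEs or for area measurement error. Section 8.1 acknowledges inaccuracy only for volume and depth, without a number. The area error of 2% to 15% below is my assumption.

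The closure rates are those behind the plan's sample size. With a two-sided alpha of 0.05 and 90% power, n per arm = [1.960 × √(2 × 0.495 × 0.505) + 1.282 × √(0.39 × 0.61 + 0.60 × 0.40)]² / 0.21², which rounds up to 118. The plan states 120, which gives power 0.907.

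**3. An ulcer that does not change.** With independent errors, one reading exceeds another with probability 1/2, whatever the size of the error. Over 12 visits, the probability of at least one reading above Baseline is 12/13 = 92%. The probability of at least one reading above the previous visit is 1 − 1/13!, or practically 100%.

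**4. Ulcers that heal and never truly grow.** Two healing models were simulated with 100,000 subjects per arm, each calibrated to 39% and 60% closure by week 12.

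- Linear model: exponential closure time T with rate −ln(1 − p)/84 per day; true area falls linearly to zero at T; lognormal error.
- Log-linear model: log area falls at a subject-specific weekly rate with mean −ln(0.02)/12 + σz_p, truncated at zero; σ is 0.15 or 0.25; closure at 2% of Baseline area.

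Subjects with at least one noise-only increase, SoC vs Galnobax (ranges in the log-linear columns run over σ):

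| Area error | Linear, vs previous visit | Linear, vs Baseline | Log-linear, vs previous visit | Log-linear, vs Baseline |
|---|---|---|---|---|
| 2% | 32% vs 13% | 9% vs 3% | 6–20% vs 2–9% | 3–16% vs 1–6% |
| 5% | 57% vs 36% | 25% vs 13% | 14–29% vs 6–14% | 5–18% vs 2–8% |
| 10% | 70% vs 52% | 39% vs 26% | 38–47% vs 22–28% | 11–23% vs 5–11% |
| 15% | not run | not run | 62–63% vs 43–45% | 17–28% vs 9–15% |

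SoC is higher in every cell. The smallest gap is 2.4 points (log-linear, σ 0.15, 2% error, vs Baseline: 3.4% vs 1.0%). The largest is 21 points (linear, 5% error, vs previous visit: 57 − 36). The reference visit matters as much as the error: in the log-linear model with σ 0.15 and 10% error, the SoC rate is 38.3% against the previous visit and 10.6% against Baseline, a factor of 3.6.

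**5. Allowing for other TEAEs.** The endpoint counts a subject once. Suppose a fraction b in each arm has another TEAE, independently of the noise events. The proportion is then b + (1 − b)q, where q is the noise-only rate, and the gap between arms is (1 − b) × (q_SoC − q_Gal).

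- b = 50%: 0.5 × 2.4 = 1.2 to 0.5 × 21 = 10.5 points.
- b = 80%: 0.2 × 2.4 = 0.5 to 0.2 × 21 = 4.2 points.

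The documents give no value for b.

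**6. Would the Section 7.2 margin serve as an AE threshold?** Requiring more than 30% over Baseline at two consecutive visits removes most noise. The false rate is at most 0.3% up to 10% error in the linear model, and at most 2.8% (SoC, 15% error) in the log-linear model. It also removes real growth. An ulcer truly 25% larger than Baseline at all 12 visits is missed in 88% of subjects at 2% error and in 56% at 5%.

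**The case against.** The strongest reply is that the plan does not oblige sites to record every measured rise. Section 8.2.7 can exclude a non-healing ulcer, partly at the investigator's discretion, and 8.1 speaks of clinically significant findings. A reader of 8.2.5 alone might infer that any increase must become an AE; with 8.2.7 in the same chapter, the documents do not support that. This part of the objection stands. It turns the defect into a contradiction plus a missing definition, and the noise mechanism operates to the extent that sites follow 8.2.5.

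A reader might also take the 21-point gap as the expected TEAE difference. That would require no subject to have any other TEAE. Section 8.2.5 makes out-of-range laboratory, vital-sign and ECG changes AEs regardless of clinical significance, so other TEAEs are likely to be common and the gap smaller.

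A third inference is that drug-related harm would be hidden. Section 9.4.4.1 already tabulates TEAEs by preferred term, severity and relationship, and Section 9.4.4 plans no formal test. Related events would be visible; only the overall proportion is distorted.

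Debridement is a weaker contributor than it may seem. The procedure in 8.1 ("Perform sharp debridement to remove all necrotic soft tissue, hyperkeratotic wound margins, bacterial burden") can enlarge the measured area, but it is done only if required, and the Baseline and treatment-visit lists in Section 8 place it before measurement. That order is not mandated, and no size was computed for the effect.

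Section 9.4.1 defers detailed methods to a separate SAP. That could settle the tables, but not what sites record.

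**Conclusion.** The point holds in this form: 8.2.5 and 8.2.7 conflict on Target Ulcer enlargement, and 8.2.5 lacks an operational definition. To the extent 8.2.5 is applied as written, measurement noise and slow healing raise the TEAE proportion more in the slower-healing arm.

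The direction is robust across both healing models, both reference visits and all assumed errors, given the plan's own closure assumption. The size is not. It is about 2 to 21 points with no other TEAEs, about 1 to 10 points with a 50% background, and about 0.5 to 4 points with an 80% background. These figures rest on assumed area error, assumed healing curves, and background events that are independent and equal in both arms. Discretion under 8.2.7 could lower the counts or make them vary by site.

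Primary efficacy is unaffected. So is the vehicle local-wound endpoint, which uses pain, edema and erythema. The consequence is a descriptive safety proportion that partly reflects efficacy. That is worth correcting but does not threaten the trial's main conclusion.

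**What to change.** 1. Reconcile 8.2.5 and 8.2.7 so that one rule applies to Target Ulcer enlargement. State the reference visit and the debridement state for the comparison.
2. In 9.4.4.1, tabulate Target Ulcer enlargement by arm as its own row, derived from the areas already recorded. Present the overall TEAE proportion both with and without AEs whose only basis is a measured size increase.

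Do not take the discontinuation margin in Section 7.2 as the AE threshold. It would miss sustained real growth (step 6 of the working), and it names no reference visit either. Worsening reported by the investigator, and infection, remain AEs.

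The cost is a wording change in two sections, one extra table and a second TEAE line. No new measurement is needed.

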3 OBJECTIVES AND ENDPOINTS

OBJECTIVES	ENDPOINTS	JUSTIFICATION FOR ENDPOINTS
Primary		

 To assess the efficacy of Galnobax® in terms of proportion of Subjects achieving Target Ulcer Closure within 12-week Treatment Phase upon application of Galnobax® plus Standard of Care as against only Standard of Care treatment, as assessed by the blinded Investigator 	
The efficacy assessment will involve Galnobax® plus Standard of Care and only Standard of Care groups
 
Efficacy endpoints:
 
Proportion of subjects achieving Target Ulcer Closure within 12-week Treatment Phase, as assessed by blinded Investigator
	Complete wound closure of a chronic, nonhealing wound is one of the most important objective and clinically meaningful wound healing endpoint
Secondary		
Efficacy	Efficacy endpoints	

 To compare Time to Target Ulcer Closure within the 12-week Treatment Phase, upon application of Galnobax® plus Standard of Care as against only Standard of Care treatment, as assessed by the blinded Investigator 	
 Time to Target Ulcer Closure during the 12-week Treatment Phase, as assessed by the blinded Investigator 	This endpoint evaluates clinically meaningful reduction in the time to Target Ulcer Closure using a time-to-event analysis (the event being first observation of complete closure)

 To compare proportion of Subjects achieving Target Ulcer Closure till End of Study upon application of Galnobax® plus Standard of Care as against only Standard of Care treatment, as assessed by the blinded Investigator 	
 Proportion of Subjects achieving Target Ulcer Closure till End of Study, as assessed by the blinded Investigator 	This endpoint is for evaluating sustained effect of the treatment post its discontinuation
Safety		

 To investigate the safety of Galnobax® treatment during the Study 	
 Proportion of Subjects with treatment emergent adverse events (TEAEs) 	This endpoint evaluates safety of Galnobax® by assessing TEAEs

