9.4.4 SAFETY ANALYSES

Safety will be analyzed for all Subjects in ITT Population in the three groups. No formal statistical analysis will be performed.

To investigate the safety of Galnobax® vehicle for establishing non-deleterious effects of Vehicle on wound healing, number and percentage of events as well as number and percentage of Subjects with events related to local wound assessment (local pain, edema, erythema) of Target Ulcer in Vehicle plus SoC group will be tabulated and reported.

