9.4.4.2 CLINICAL LABORATORY TEST

The clinical laboratory tests will be summarized descriptively for each of the continuous parameter at Subject's visits when tests are carried out for the changes from the baseline parameter. Shift tables in terms of counts and percentages will be presented at each relevant visit versus baseline for categorical laboratory parameters.

Individual data listings of laboratory results will be presented for each Subject. Clinically significant laboratory test abnormalities that are considered AEs by the Investigator will be presented in the AE listings.

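### The adverse-event threshold for laboratory, vital-sign and ECG abnormalities differs between Sections 8.2.5, 9.4.4.2 and 8.1, so the overall TEAE proportion depends on the rule followed and is likely to be inflated and diluted under 8.2.5

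*Combined protocol and SAP*

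**What the plan says.** **Section 8.2.5 (Adverse Event Reporting).** A change from Baseline in laboratory values, vital signs or ECG parameters "outside accepted or normal range will be reported as adverse event irrespective of" how clinically significant the Investigator judges it to be.

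**Section 9.4.4.2 (Clinical Laboratory Test).** "Clinically significant laboratory test abnormalities that are considered AEs by the Investigator will be presented in the AE listings".

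**Section 8.1 (Recording and Assessment of adverse events).** The trigger for recording an AE is "if there is any clinically significant abnormality or signs or symptom detected in the Subject", or reported by the Subject, after treatment is applied.

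**Section 8.2.4.** A condition present at screening or "before application of first dose will be considered as baseline and not reported as an AE", unless it deteriorates. Section 8.2.7 also excludes progression of the underlying disease, at the Investigator's discretion.

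**Section 9.4.4.1.** TEAEs are "defined as all AEs on or after the application of first dose of IP"; there is no filter for clinical significance. Section 3 lists the proportion of Subjects with TEAEs as the only endpoint for the Galnobax safety objective.

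**Section 9.4.4.** For safety, "No formal statistical analysis will be performed".

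**The concern.** Section 8.2.5 removes the Investigator's judgement from the decision that an out-of-range value is an AE. Section 9.4.4.2 presumes that this judgement has been made. Since every AE from first dose is a TEAE, the choice of rule passes straight into the safety endpoint.

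Two things are at stake. First, with approximately 40 sites (Section 4.1), some may work from 8.2.5 and others from 8.1, and the pooled proportion would then partly reflect site practice. Second, if all sites follow 8.2.5, incidental out-of-range values raise the proportion in every arm, and any real difference in clinical events is compressed.

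**Working it through.** The plan states no expected TEAE rate, no out-of-range rate and no power for safety, so there is no figure of its own to reproduce. The sample size in Section 9.2 concerns the efficacy endpoint only.

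**1. How often the broad rule is tested.** Section 8.1 and the Schedule of Activities list 10 haematology and 14 biochemistry parameters, tested at four occasions after first dose (V6, V10, V14 or EOT, V18 or EOS). HbA1c is measured at two of these. Random glucose and vital signs are taken at 16 visits (V3 to V18), and ECG on four occasions. Counting systolic and diastolic pressure separately, vital signs give 5 values per visit. The maximum per Subject is

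(10 + 14) × 4 + 2 + 16 + 5 × 16 + 4 = 96 + 2 + 16 + 80 + 4 = 198 measurements.

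Early closure or discontinuation reduces this.

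**2. Share of no-effect Subjects with a newly out-of-range laboratory value.** These inputs are assumptions: 95% reference ranges (out of range if |z| > 1.96), one baseline and four later tests, and independent analytes with within-subject correlation ρ between visits. An analyte counts only if it is in range at baseline and out of range later, so values already abnormal at baseline do not count. Simulated share with at least one such analyte:

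| Independent analytes | ρ = 0.5 | ρ = 0.7 | ρ = 0.9 |
|---|---|---|---|
| 24 | 0.967 | 0.914 | 0.723 |
| 10 | 0.757 | 0.636 | 0.416 |

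The 10-analyte row is there because several parameters are linked (haemoglobin, haematocrit, red cell count and the red cell indices, for example), so 24 independent analytes is an upper case. The range is about 42% to 97%. Vital signs, ECG and weekly glucose are left out and could only add to it.

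**3. A cruder check with wider assumptions.** If a share r of measurements is newly out of range and m measurements are independent, the share of Subjects affected is 1 − (1 − r)^m.

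- All 198 measurements: 33% at r = 0.2%, 86% at r = 1%, about 100% at r = 5%.
- Each of 32 distinct parameters counted once (24 laboratory, HbA1c, random glucose, 5 vital-sign values, ECG): 6% at r = 0.2%, 28% at r = 1%, 81% at r = 5%.

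The 6% figure needs both a very low rate and complete correlation across visits. Under the 95% ranges of step 2, r is 2.0% to 4.1%. Counting the 32 parameters once then gives 1 − 0.980^32 = 48% to 1 − 0.959^32 = 74%.

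**4. Dilution.** Let a share q of each arm have a TEAE from incidental values alone, independently of clinical events. A clinical TEAE rate p is then observed as 1 − (1 − p)(1 − q), and a difference shrinks by the factor (1 − q). For assumed clinical rates of 30% and 20%:

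| q | Observed rates | Difference |
|---|---|---|
| 0 | 30.0% vs 20.0% | 10.0 points |
| 0.42 | 59.4% vs 53.6% | 5.8 points |
| 0.72 | 80.4% vs 77.6% | 2.8 points |
| 0.97 | 97.9% vs 97.6% | 0.3 points |

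**The case against.** A reader might infer that the endpoint saturates and cannot show a safety difference, and that no site can comply with all three sections. The documents do not support that much.

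- **Section 8.1 contains no word limiting AEs to clinically significant findings.** It gives a sufficient condition. A site that follows 8.2.5 also records everything 8.1 asks for. Section 9.4.4.2 describes what the listings will show and does not instruct sites. The direct conflict is therefore between the collection rule of 8.2.5 and the reporting text of 9.4.4.2. This stands.
- **Pre-existing abnormality is carved out.** The rule concerns change from Baseline, and Sections 8.2.4 and 8.2.7 exclude stable pre-existing conditions and disease progression. Long-standing hyperglycaemia, anaemia or low eGFR need not count. This stands, though step 2 already leaves out values abnormal at baseline.
- **Saturation is an assumption.** At 42% there is no ceiling; at 97% there is. The documents do not say which applies. This stands.
- **Safety is descriptive.** No planned test loses power. Section 9.4.4.1 also tabulates TEAEs by system organ class and preferred term, severity and relationship, with SAEs and deaths. Sections 9.4.4.2 and 9.4.4.3 summarise laboratory values and vital signs separately. Signals can still appear there. This limits the harm, but incidental values enter the severity and relationship tables too, and no breakdown shows which rule a site used.
- **Inclusive capture may be deliberate.** It avoids a subjective call on significance. That is a fair reason to keep capturing everything, but it does not explain 9.4.4.2.
- **A separate SAP is still to come (Section 9.4.1).** It may set counting rules. It could apply a significance filter only if sites have recorded the judgement consistently, which the present text does not secure.

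**Conclusion.** The inconsistency is in the text and feeds the only endpoint named for the Galnobax safety objective. Under 8.2.5 the overall TEAE proportion is likely to be inflated in all arms and any difference diluted. With the assumed reference ranges, analyte counts and correlations, 42% to 97% of no-effect Subjects would have a newly out-of-range laboratory value, and a 10-point difference would shrink to between 5.8 and 0.3 points. These figures are only as good as those assumptions.

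The damage is to the headline proportion. It does not extend to safety assessment as a whole or to the primary efficacy analysis. The point should be settled before sites record AEs, because mixed practice is hard to undo afterwards.

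**What to change.** 1. Reconcile 8.1, 8.2.5 and 9.4.4.2 to one written rule before sites record AEs.
2. Keep capturing every out-of-range change from Baseline, with a flag for clinically significant (CS) or not clinically significant (NCS). Section 9.4.4.3 already uses this classification for the physical examination.
3. Report as the headline the proportion of Subjects with TEAEs excluding abnormalities that are only NCS, and show the all-inclusive proportion beside it.
4. Add by-arm summaries of out-of-range post-baseline vital-sign and ECG values. Moving NCS findings to the existing tables would not be enough. The shift tables in 9.4.4.2 cover only categorical laboratory parameters, vital signs have summaries and listings only, and no post-baseline ECG table is named. For a beta-blocker, NCS ECG changes would lose their only specified tabulation.

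The cost is a short amendment, one CRF flag and a few extra tables. The downside is that the headline proportion depends on the blinded Investigator's CS/NCS call; showing the all-inclusive figure alongside offsets this.
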